#### **6.8.4. Clinical Laboratory Evaluation**

A shift table will present the number and percentage of patients in each cell resulting from cross-tabulating the status (low, normal, and high) of the highest/lowest post-baseline value versus that of the Baseline for each laboratory test, if applicable, by analysis period and treatment group as defined in Section 5.1. If a specific test can have both a significant low and high, then a shift table will be generated for each direction. The percentage will be based on the total number of patients in the Safety Set. A status of missing may be added, if necessary. This analysis will be repeated for last post-baseline result.

Only the highest value will be summarized for alanine aminotransferase (ALT), alkaline phosphatase, amylase, aspartate aminotransferase (AST), C-reactive protein, creatine kinase, creatinine, cystatin C, gamma glutamyl transferase (GGT), lactate dehydrogenase (LDH), total bilirubin, uric acid, absolute basophils, absolute eosinophils, basophil percent, eosinophil percent, activated partial thromboplastin time, international normalized ratio, prothrombin time, and urine KIM-1, and urine protein. Only the lowest value will be summarized for albumin, and platelets. Both the highest and lowest values will be summarized for blood urea nitrogen (BUN), calcium, chloride, glucose, potassium, sodium, absolute lymphocytes, absolute monocytes, absolute neutrophils, hematocrit, hemoglobin, lymphocyte percent, monocyte percent, neutrophils percent, white blood cell (WBC) count, and urine pH and specific gravity.

The frequency and percentage of patients meeting the potentially clinically significant abnormality criteria (defined in [Appendix Table 1](#), [Appendix Table 2](#), [Appendix Table 3](#)) at any time point post-baseline will be summarized by Analysis Period and treatment group. Additionally, the total number of potentially clinically significant abnormalities will be summarized.

Baseline value, highest/lowest value and last observation and the corresponding change from Baseline will be summarized by Analysis Period and treatment group.

All patient-level clinical laboratory values will be displayed in data listings. In addition, values meeting the potentially clinically significant abnormalities criteria will be presented in data listings. Treatment-emergent abnormalities will be indicated in the listing.

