9.8. Safety Considerations

9.8.1. General Safety Precautions

This study is being conducted at clinical trial centers equipped with state of the art medical equipment. Trained medical personnel will be present during the entire dosing period and for at least 1 hour after each dose to monitor each patient. If the patient has not experienced an infusion reaction after 48 weeks of open-label treatment, the Investigator has discretion to reduce the post-infusion observation period to 30 minutes. Resuscitation equipment will be readily available for immediate use during dose administration and follow-up, and patients will not be allowed to leave the clinic until the investigator or designated physician has ascertained that they can do so safely.

Safety assessments will include routine clinical and laboratory evaluations. Refer to Section 9.8.2 and to the schedules of events (Table 2). In addition, ECGs and ECHOs will be performed as outlined in the schedules of events.

The most likely potential drug-related AEs based on the nonclinical safety profile of SRP-4045 are expected to be related to renal function. These potential events are readily monitored through assessment of protein in the urine and by monitoring changes in serum creatinine and/or blood urea nitrogen (BUN). In addition, serum cystatin C will be used as a safety biomarker for renal clearance due to the inherently low creatinine levels in DMD patients. Kidney function will also be assessed using the urine biomarker kidney injury molecule-1 (KIM-1) (Han 2002).

CCI

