9.8.3. Stopping Rules

Safety data review including AEs and laboratory assessments will be performed on an ongoing basis. The stopping rules discussed in this section will apply only to the dose titration period of the study. If dosing of an individual patient is suspended during the open-label period, the Investigator will consult with the Medical Monitor to determine whether the patient may resume treatment or whether he needs to be excluded from further dosing.

During the study, sites are required to report all AEs as defined in Section 9.8.2 and Section 10.4. If safety concerns arise at any time, dosing may be stopped until these concerns have been addressed. Dosing will be interrupted to allow for review of cumulative safety data by the DSMB if any of the following conditions are met:

- >2 severe AEs or ≥ 3 moderate AEs considered to be possibly/probably or definitely related to investigational drug product
- Any SAE considered to be possibly/probably or definitely related to investigational drug product
- ≥ 2 patients develop 2 consecutive serum creatinine levels $\geq 2X$ their respective average pre-treatment values
- ≥ 2 patients develop 2 consecutive instances of unexplained protein in urine $>2+$

- Any unexplained gamma glutamyl transferase (GGT) >3X upper limit of normal (ULN) in combination with bilirubin >2X ULN
- 2 consecutive instances of unexplained activated partial thromboplastin time (aPTT) >45 seconds in the same patient

During the dose titration period of the study, the DSMB will be notified by the Sponsor within 24 hours of the Sponsor learning of any of the events listed above. Dosing may also be interrupted or halted if warranted at the discretion of the Sponsor or Investigator. Any decisions related to dose adjustment, delay, or stopping during dose titration will be communicated by the Sponsor to all sites immediately. In addition, Investigators may, in the event of an emergency, directly contact their peers at other sites to communicate safety concerns.

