### **Baseline**

Double-Blind Period (safety): Baseline will be defined as the last value prior to the first dose of study drug (casimersen or placebo) administration.

Casimersen Period (safety): Baseline will be defined as the last value prior to the first dose of casimersen administration.

Combined Double-Blind and Open-Label Period (efficacy): Baseline will be defined as the last value prior to the first dose of study drug (casimersen or placebo) administration.

CCI

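### The SAP's creatinine abnormality criteria have no baseline-relative rule, so a doubling from a low baseline is not counted in the incidence table

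*SAP*

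**What the plan says.** **Protocol.** Section 9.8.1 states that the most likely drug-related adverse events "are expected to be related to renal function". It adds that "serum cystatin C will be used as a safety biomarker for renal clearance due to the inherently low creatinine levels in DMD patients". Section 9.8.3 interrupts dosing for review by the Data Safety Monitoring Board (DSMB) during titration if at least "2 patients develop 2 consecutive serum creatinine levels" at or above twice "their respective average pre-treatment values". Section 7.3 makes the incidence of clinical laboratory abnormalities a component of the primary endpoint.

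**SAP.** Section 6.8.4 tabulates "The frequency and percentage of patients meeting the potentially clinically significant abnormality criteria" at any post-baseline time point, by Analysis Period and treatment group, and refers to Appendix Tables 1 to 3. The creatinine row of Appendix Table 1 has two entries: a predefined increase of 35 µmol/L, and a markedly abnormal criterion of any value above the ULN. In the same table, AST, ALT, LDH, creatine phosphokinase, GGT and BUN each have a criterion that includes a multiple of baseline. For BUN it is combined with exceeding the ULN; for GGT it is an alternative to exceeding the ULN.

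The reference value also differs between the documents. The protocol uses the average of pre-treatment values. SAP 5.8 says for the double-blind period: "Baseline will be defined as the last value prior to the first dose of study drug (casimersen or placebo) administration". For the Casimersen Period the SAP uses the last value before the first casimersen dose.

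**The concern.** Both SAP creatinine thresholds are absolute: one is a fixed increment, the other a population limit. The protocol's threshold is relative to the patient. In patients whose creatinine starts low, a relative rise can be large while the absolute value stays unremarkable. The patients the protocol singles out as having low creatinine are therefore those in whom the SAP's creatinine criteria are least sensitive.

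At stake is the incidence count for a marker of the organ system the protocol names as the main expected risk, within a primary-endpoint component. The stopping rules in Protocol 9.8.3 apply only to titration. Protocol 8.3 anticipates about 128 weeks of open-label treatment for the last patient enrolled, and over that time the SAP tables are the systematic creatinine tally.

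**Working it through.** The plan has no figure of its own to reproduce here: the documents give no creatinine ULN and no baseline values. The check is of the thresholds.

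**Inputs.**
- From SAP Appendix Table 1: a rise of 35 µmol/L, or a value above the ULN.
- From Protocol 9.8.3: a value at least 2 times the patient's own pre-treatment average.
- Assumed: ULN of 45, 62, 80 or 106 µmol/L, and baseline b of 10 to 40 µmol/L.

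**Step 1: the condition.** A patient who exactly doubles goes from b to 2b, a rise of 2b − b = b. If either SAP criterion is enough, the patient is counted when b ≥ 35 or 2b > ULN. The patient is not counted when b < 35 and 2b ≤ ULN, that is, when b < 35 and b ≤ ULN/2.

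**Step 2: the range missed.** Section 6.8.4 does not say which column of Appendix Table 1 defines a potentially clinically significant value, so two readings are shown.

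| Assumed ULN (µmol/L) | ULN/2 | Doubling not counted, either criterion suffices | Doubling not counted, markedly abnormal column only |
|---|---|---|---|
| 45 | 22.5 | b ≤ 22.5 | b ≤ 22.5 |
| 62 | 31 | b ≤ 31 | b ≤ 31 |
| 80 | 40 | b < 35 | b ≤ 40 |
| 106 | 53 | b < 35 | b ≤ 53 |

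If only the predefined-change column is used, the gap is b < 35 at every ULN. If both columns must be met, it is b < 35 or b ≤ ULN/2, whichever reaches further. A gap exists on every reading.

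**Step 3: an example.** With b = 20, a doubling gives 40. The rise is 20, below 35, and 40 does not exceed any of the assumed ULNs. The patient meets the protocol's per-patient level but neither SAP criterion.

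**Step 4: the fold rise at which the SAP criteria first engage.** With either criterion sufficient, this is the smaller of (b + 35)/b and ULN/b. On the ULN route the value must exceed the limit.

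| b (µmol/L) | (b + 35)/b | First engaged, ULN 45 | First engaged, ULN 62 | First engaged, ULN 80 or 106 |
|---|---|---|---|---|
| 10 | 4.50 | 4.50 | 4.50 | 4.50 |
| 15 | 3.33 | 3.00 | 3.33 | 3.33 |
| 20 | 2.75 | 2.25 | 2.75 | 2.75 |
| 25 | 2.40 | 1.80 | 2.40 | 2.40 |
| 30 | 2.17 | 1.50 | 2.07 | 2.17 |

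**Step 5: whether another table supplies the count.** The creatinine shift table in 6.8.4 classes the highest value as low, normal or high. A doubling that stays at or below the ULN is never high. It may show as low-to-normal, or not change category at all. The change-from-baseline summary is absolute: a rise of 20 is a doubling from 20 but a 1.5-fold rise from 40 (60/40). Neither table gives the number of patients who doubled.

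**The case against.** The strongest reply is that nothing is hidden. SAP 5.1 includes the maximum among the descriptive statistics, and 6.8.4 applies these to the highest creatinine value and its change from baseline. With 8 and 4 patients, the largest individual rise is therefore printed. All patient values are listed, and the protocol synopsis plans review of individual values. The protocol's stated answer to low creatinine is cystatin C, and the SAP counts cystatin C above the ULN. BUN, urine protein above 1+ and a renal adverse event of special interest are tallied separately, and the highest KIM-1 is summarised. The synopsis also says laboratory abnormalities rest on predefined normal ranges, which a ULN criterion follows. A rule that prompts DSMB review need not be an endpoint definition.

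Most of this stands, and it limits the point to missing incidence. It does not supply that incidence. The cystatin C criterion is also ULN-based, the BUN criterion requires exceeding the ULN as well, and KIM-1 has no criterion in Appendix Tables 1 to 3. The renal event category depends on adverse event reporting, and under Protocol 11.2.1 a test abnormality is an adverse event when it alters medical care.

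Three stronger readings are tempting and are not supported:
- A reader might infer that the SAP would conceal a dosing interruption. The protocol has the DSMB notified of such events, and the values remain in the listings.
- A reader might infer that one patient who doubles meets the interruption condition. It takes at least two patients with two consecutive values each.
- A reader might infer that the protocol chose the twofold rule because creatinine is low in DMD. Section 9.8.3 gives no reason for it.

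**Conclusion.** The point holds in conditional form. SAP 6.8.4 and Appendix Table 1 do not count an exact doubling of creatinine when b is below 35 µmol/L and 2b is at or below the ULN, and no other planned table gives the incidence of doubling. That conclusion follows from the documents alone.

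How many of the 12 patients fall in this range cannot be determined, because the ULN and baselines are assumptions. The missed range is narrower at a lower ULN, which matters in a population that starts at age 7. Rises well above twofold can still be caught by the 35 µmol/L criterion, so not every large rise is missed.

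This is a gap in tabulation within a descriptive study, not a loss of safety data and not a fault in the stopping rule. It merits a small SAP change because it concerns the protocol's named risk and a primary-endpoint component.

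**What to change.** Add to the creatinine row of Appendix Table 1 a criterion of a value at least 2 times the patient's pre-treatment value, and keep the two existing criteria. Tabulate patients with any occurrence and patients with two consecutive occurrences, by Analysis Period and treatment group.

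Define the terms in the SAP:
- **Reference, double-blind period:** the average of values before the first dose of study drug, to match the protocol. The SAP does not currently derive this average.
- **Reference, Casimersen Period:** the SAP Baseline, the last value before the first casimersen dose. Label the tables so that the two references are not confused.
- **Consecutive:** consecutive available results, including unscheduled repeats. SAP 5.7 leaves unscheduled safety values out of by-time-point summaries, so this must be explicit. After Week 36 scheduled laboratory tests are 12 weeks apart, so a footnote should say that two consecutive results span a longer interval there than during titration.

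The cost is SAP wording, one derived reference value and two table rows, from data already collected. This is a reporting change only and does not alter the protocol's stopping rule. The downside is that at very low baselines a small absolute change can be a doubling, so a few more patients may be flagged; the consecutive row limits this.

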7.3. Study Endpoints

The following study endpoints will be evaluated in this study. Descriptions of all study assessments and procedures are provided in Section 10.

The primary endpoint is assessment of the safety of SRP-4045 during the double-blind dose-titration period according to the following:

- Incidence of AEs

- Incidence of clinical laboratory abnormalities (hematology, chemistry, coagulation, urinalysis)
- Incidence of abnormalities in vital signs and physical examinations
- Clinically significant worsening of ECGs and ECHO

The secondary endpoint is to determine the PK profile of SRP-4045 during the double-blind dose-titration period:

[figure not shown]
- Maximum plasma concentration (C_{max})
- Time to maximum plasma concentration (T_{max})
- Area under the plasma concentration-curve (AUC)
- Apparent volume of distribution at steady state (V_{ss})
- Elimination half-life ($t_{1/2}$)
- Total clearance (CL)
- Mean residence time (MRT)
- Urinary clearance (CL_R)

CCI

[figure not shown]

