### **Treatment-emergent Laboratory Abnormality**

A treatment-emergent laboratory abnormality will be defined as any laboratory abnormality occurring or worsening after the initiation of study drug dosing and within 28 days of the last dose of study drug.

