#### **6.8.5. Vital Signs and Other Physical Findings**

The frequency and percentage of patients meeting any of the potentially clinically significant abnormality criteria (defined in [Appendix Table 4](#)) at any time point post-baseline will be summarized by Analysis Period and treatment group as defined in Section 5.1. Additionally, the total number of potentially clinically significant abnormalities will be summarized.

Baseline value, highest/largest absolute change and last observation and the corresponding change from Baseline will be summarized by analysis period and treatment group. The largest absolute change from Baseline will be summarized for systolic blood pressure, diastolic blood pressure, and respiratory rate, and the highest value for pulse and temperature. If the largest absolute change from Baseline occurs in

both directions equally, then the higher value will be summarized. The highest/largest absolute change value will not be summarized for height, weight, BMI, ulnar length, or calculated height. Only results that occurred within 28 days of the last dose of study drug, or before initiation of a new study drug will be included.

Vital signs will be listed for all patients. In addition, values meeting the potentially clinically significant criteria will be presented in a data listing. Treatment-emergent abnormalities will be indicated. Height and weight will also be listed.

[figure not shown]

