## 9. APPENDICES: Criteria of Abnormalities

**Appendix Table 1 Chemistry Laboratory Abnormalities of Interest**

Test	Unit	Predefined Change		Markedly Abnormal Criteria
		Decrease	Increase	
Fasting blood glucose a	mmol/L	3.1	3.2	NA
BUN	mmol/L	NA	NA	Value $>1.5 \times$ Baseline and $>\text{ULN}$
Creatinine	$\mu\text{mol/L}$	NA	35	Value $>$ ULN
Sodium	mmol/L	8	8	NA
Potassium	mmol/L	1.1	1.0	Value $> 5.5 \text{ mmol/L}$ or $< 3 \text{ mmol/L}$
Chloride	mmol/L	9	8	NA
Uric acid	$\mu\text{mol/L}$	NA	NA	$>1 \times \text{ULN}$
Calcium b	mmol/L	0.30	0.30	NA
AST (SGOT)	U/L	NA	NA	Value $\geq 3 \times$ Baseline Value
ALT (SGPT)	U/L	NA	NA	Value $\geq 2 \times$ Baseline Value
Gamma glutamyl transferase	U/L	NA	NA	Value $> 3 \times$ Baseline OR $>$ ULN
Alkaline phosphatase	U/L	NA	NA	Value $> 1.5 \times \text{ULN}$
Albumin c	g/dL	1	1	$<$ LLN or $>$ ULN
Total bilirubin d	$\mu\text{mol/L}$	NA	10	Value $> 1.5 \times \text{ULN}$
Lactate dehydrogenase	U/L	NA	NA	Value $\geq 2 \times$ Baseline Value
Creatine phosphokinase	U/L	NA	NA	Value $\geq 2 \times$ Baseline Value
Cystatin C	mg/L	NA	NA	$>$ ULN

aConvert to SI unit by multiplying mg/dL value by 0.0555

bmultiply mg/dL value by 0.25;

cmultiply g/dL value by 10

dmultiply mg/dL value by 17.1.

ALT = alanine aminotransferase; AST = aspartate aminotransferase; BUN = blood urea nitrogen; LLN = lower limit of normal; NA = Not Applicable; ULN = upper limit of normal

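### SAP 6.8.4 counts unchanged pre-existing laboratory abnormalities as events for the 19 of 28 tests with an absolute limit, because the incidence table does not use the treatment-emergent definition in 5.8

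*SAP*

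**What the plan says.** Protocol 7.3 makes the incidence of clinical laboratory abnormalities in the double-blind period a component of the primary endpoint. SAP 6.8.4 provides the table: patients meeting a potentially clinically significant criterion in Appendix Tables 1-3 "at any time point post-baseline will be summarized by Analysis Period and treatment group". The total number of such abnormalities is reported as well.

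SAP 5.8 separately defines a treatment-emergent laboratory abnormality as "any laboratory abnormality occurring or worsening after the initiation of study drug dosing and within 28 days of the last dose of study drug". In 6.8.4 this definition is used once: "Treatment-emergent abnormalities will be indicated in the listing".

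Two other parts of 6.8.4 take account of Baseline. A shift table by low/normal/high status sets "the highest/lowest post-baseline value versus that of the Baseline for each laboratory test", and is repeated for the last value. Baseline, extreme and last values are also summarised with change from Baseline.

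For vital signs, SAP 6.8.5 adds a restriction that 6.8.4 lacks, and 6.8.6 repeats it for ECG and ECHO: "Only results that occurred within 28 days of the last dose of study drug, or before initiation of a new study drug will be included".

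**The concern.** The SAP holds two rules for who has a laboratory abnormality, and the looser one drives the reported incidence. Where a criterion is a fixed limit, a patient who entered the study beyond it and did not change appears in the table exactly as a patient who crossed it on drug.

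With 8 patients against 4, one such patient visibly moves a percentage. The Casimersen Period (SAP 5.1) has a single group, so no comparator column is there to show how much of the count was present beforehand. The affected tests include creatinine, cystatin C and urine protein, which bear on the renal effects that Protocol 9.8.1 names as the most likely drug-related events.

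**Working it through.** The plan states no figure to reproduce here: SAP 4.2 has no formal sample size calculation and Protocol 12.4.7 makes the safety analyses descriptive. The check is a row-by-row reading of the Appendix, then a comparison with the shift tables.

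**1. Which criteria can be met with no change from Baseline?**

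| Appendix table | Rows | Absolute limit | Change from Baseline required |
|---|---|---|---|
| 1 Chemistry | 17 | 8: creatinine, potassium, uric acid, GGT (through its alternative of above ULN), alkaline phosphatase, albumin, total bilirubin, cystatin C | 9: glucose, BUN, sodium, chloride, calcium, AST, ALT, LDH, CPK |
| 2 Hematology | 10 | 10 | 0 |
| 3 Urinalysis | 1 | 1: protein | 0 |
| Total | 28 | 19 | 9 |

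**2. Weight of one unchanged patient.** Group sizes are from SAP 4.2.
- Casimersen, double-blind: 1/8 = 12.5 points.
- Placebo, double-blind: 1/4 = 25 points.
- All casimersen-treated: 1/12 = 8.3 points.

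**3. What the shift tables recover.** Fifteen absolute limits sit exactly at ULN or LLN:
- above ULN: creatinine, uric acid, GGT, cystatin C (4);
- albumin, both sides (2);
- below LLN: hematocrit, hemoglobin, red cells, white cells, lymphocytes, monocytes, eosinophils (7);
- basophils, both sides (2).

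For these, a move from normal to high or low is new onset, and high-to-high or low-to-low is pre-existing. But 6.8.4 restricts direction: albumin is summarised for the lowest value only, basophils and eosinophils for the highest only, and red cells appear in none of its three lists. So 15 - 4 = 11 limits are recovered. The four that are not are albumin above ULN, basophils below LLN, eosinophils below LLN and red cells below LLN.

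Cut-offs away from ULN or LLN are not recovered by low/normal/high status either: potassium; alkaline phosphatase and bilirubin at 1.5 × ULN; the upper limits for white cells, eosinophils and neutrophils; the lower neutrophil limit; platelets; and urine protein above 1+.

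**4. The total count.** SAP 6.8.4 does not say whether the total counts values or patients. Protocol 7.1 schedules laboratory tests at Weeks 2-9 and 12, so 8 + 1 = 9 post-baseline samples by Week 12. If values are counted, one unchanged patient can add up to 9 abnormalities per test by then.

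**5. How likely is an affected patient?** The documents give no Baseline prevalence. Purely as an assumption, with p the per-test prevalence, the chance of at least one already-abnormal patient is 1 - (1 - p)^n:

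| p | n = 8 | n = 4 |
|---|---|---|
| 5% | 34% | 19% |
| 10% | 57% | 34% |
| 20% | 83% | 59% |
| 30% | 94% | 76% |

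This shows sensitivity to p and is not an estimate for this trial.

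**6. Would a bare rule of worse than Baseline solve it?** Take a persistently abnormal patient with a continuous test and exchangeable draws (assumption). Baseline is the most extreme of 10 values with probability 1/10, so at least one of the 9 later draws is worse with probability 9/10. Most such patients would still be counted.

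**The case against.** The strongest reply is that 6.8.4 already separates new from pre-existing status through its shift tables and also gives change from Baseline. This stands for 11 of the 15 limits set at ULN or LLN, and it is why the point is an improvement and not a serious defect. It does not cover the limits and the total identified above, and a flag in a listing is not an incidence.

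A second reply is that the table matches the stated endpoint. SAP 4.4.1 writes treatment-emergent for adverse events but not for laboratory abnormalities, and 6.8.5 counts vital signs at any post-baseline time too. This also stands: a reader might infer that 6.8.4 contradicts the endpoint, and it does not. Still, Protocol 12.4.7 plans shift and frequency tables of predefined change in abnormal values, which sits better with a change-based count.

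Third, the consequence is limited. No test is planned on this table, and with 12 patients the flagged listing can be read in full. A reader might infer that the count alone could create or hide a drug signal; beside shift tables, change from Baseline and flagged listings, that goes too far.

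Fourth, some tests may rarely be abnormal at entry. Protocol 9.8.1 notes low creatinine in DMD, and exclusion 11 removes clinically significant hepatic, renal and hematologic illness. That lowers the likely count for some tests but does not exclude values just outside a reference bound.

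**Conclusion.** The point holds in a limited form. For the 19 tests with an absolute limit, the 6.8.4 table and total mix pre-existing with new abnormalities. Each unchanged patient adds 12.5, 25 or 8.3 points according to the group. This follows from the text and the group sizes alone. The gap not filled elsewhere in the section consists of four limits at ULN or LLN, the cut-offs away from ULN or LLN, and the total count.

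Three stronger readings are not supported:
- **All laboratory tests are affected.** Nine of the 28 rows require a change from Baseline.
- **A third to a half of patients enter with a countable abnormality.** A reader might pool the 15 limits at ULN or LLN, with tails of 2.5% or 5%, and get 1 - 0.975^15 = 32% or 1 - 0.95^15 = 54%. The tail rates are not in the documents, no pooled any-test row is specified, and independence is implausible for hematocrit, hemoglobin and red cells.
- **The missing 28-day window inflates the counts.** Follow-up is about 4 weeks after the last infusion (Protocol 8.3) and early-termination assessments fall within 30 days of withdrawal (Protocol 8.4), so its effect is close to nil.

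**What to change.** Amend SAP 6.8.4 as follows.
- For each criterion, report the number of patients who newly meet it after that Analysis Period's Baseline, with the number meeting it at Baseline alongside. For the Casimersen Period, count onset from Casimersen Day 1, which matches that period's Baseline in 5.8.
- Count a patient who met the criterion at Baseline only if a pre-specified worsening threshold for that test is reached, not on any value worse than Baseline. Appendix Table 1 already lists a predefined change for creatinine, potassium, albumin and total bilirubin, which could serve as a starting point; the other 15 absolute-limit tests need a threshold agreed.
- Base the total number of abnormalities on the newly met criteria, and state whether it counts values or patients.
- Keep the any-post-baseline count as a second column, so that nothing now planned is lost.

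The cost is SAP wording, an agreed threshold for each absolute-limit test, slightly more output and smaller headline counts. No new data are needed, and the listing already requires a treatment-emergent flag.
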